5.4.7. Definition, Procedures, and Supportive Care Guidelines for Immune-Related Adverse Events

INCAGN01876 is an immune modulator, and although no toxicities were identified in preclinical models, it is possible that irAEs (both nonserious and serious) similar to those described with approved immunotherapies may occur. Adverse events of a potential immunologic etiology or irAEs may be defined as an AE consistent with an immune phenomenon associated with drug exposure *after all other etiologies have been eliminated*. Immune-related AEs may be expected based on the nature of INCAGN01876, its mechanism of action, and based on reported experience with other immunotherapies. Special attention should be paid to AEs that may be suggestive of potential irAEs. An irAE can occur shortly after the first dose or several months after the last dose of treatment. Suspected irAEs should be discussed with the medical monitor when possible.

Subjects should receive appropriate supportive care measures as deemed necessary by the treating investigator. Suggested supportive care measures for the management of drug-related AEs with potential immunologic etiology are outlined in Table 5. Detailed supportive care guidelines for specific irAEs can be found in Appendix B. For each AE, attempts should be made to rule out other causes, including but not limited to metastatic disease or bacterial or viral infection, which might require specific supportive care.

Table 5: Supportive Care Guidelines for Subjects Exhibiting Immune-Related Adverse Events

CTCAE Grade/Severity	Supportive Care^a
Grade 1 (mild)	
• Monitor symptoms and provide symptomatic treatment.
Grade 2 (moderate)	
• Monitor symptoms and provide symptomatic treatment.• Consider consultation with specialists as necessary.• Consider systemic corticosteroids per institutional standard of care.
Grade 3-4 (severe–life-threatening)	
• Monitor symptoms and provide symptomatic treatment.• Consider consultation with specialists as necessary.• Administer corticosteroids per institutional standard of care.• More potent immunosuppressive therapies should be considered for events not responding to systemic steroids after discussing with the medical monitor.• Study drug should be permanently discontinued for clinically significant or severe irAEs, or for events where steroid course cannot be tapered below 7.5 mg/day prednisone or equivalent to manage symptoms.

^a Detailed supportive care guidelines for specific irAEs can be found in [Appendix B](#).

5.4.8. Management of Infusion Reactions

[Table 6](#) shows treatment guidelines for subjects who experience an infusion reaction associated with administration of study drug. Signs and symptoms usually develop during or shortly after drug infusion and generally resolve completely within 24 hours of completion of infusion.

Table 6: INCAGN01876 Infusion Reaction Treatment Guidelines

CTCAE Grade	Treatment	Premedication at Subsequent Dose Administration

Grade 1: Mild reaction; infusion interruption not indicated; intervention not indicated.
	
Increase monitoring of vital signs as medically indicated until the subject is deemed medically stable in the opinion of the investigator.
	
None.

Grade 2: Requires infusion interruption but responds promptly to symptomatic treatment (eg, antihistamines, NSAIDs, narcotics, IV fluids); prophylactic medications indicated for ≤ 24 hours.
	
Stop infusion and monitor symptoms. Additional appropriate medical therapy may include but is not limited to the following:
 
 • IV fluids • Antihistamines • NSAIDs • Acetaminophen • Narcotics 
Increase monitoring of vital signs as medically indicated until the subject is deemed medically stable in the opinion of the investigator.
 
If symptoms resolve within 1 hour of stopping drug infusion, the infusion may be restarted at 50% of the original infusion rate. Otherwise, dose administration will be interrupted until symptoms resolve, and the subject should be premedicated for the next scheduled dose.
 
Subjects who develop Grade 2 toxicity despite adequate premedication should be permanently discontinued from further study drug administration.
	
Subject may be premedicated 1.5 h (± 30 min) prior to infusion with the following:
 
 • Diphenhydramine 50 mg orally (or equivalent dose of antihistamine). • Acetaminophen 500-1000 mg orally (or equivalent dose of antipyretic).

Grade 3: Prolonged (ie, not rapidly responsive to symptomatic medication and/or brief interruption of infusion); recurrence of symptoms following initial improvement; hospitalization indicated for other clinical sequelae (eg, renal impairment, pulmonary infiltrates).
	
Stop infusion. Additional appropriate medical therapy may include but is not limited to:
 
 • IV fluids • Antihistamines • NSAIDs • Acetaminophen • Narcotics • Oxygen • Pressors • Corticosteroids • Epinephrine 	
No subsequent dose.

Grade 4: Life-threatening; pressor or ventilatory support indicated.
	
Increase monitoring of vital signs as medically indicated until the subject is deemed medically stable in the opinion of the investigator.
 
Hospitalization may be indicated.
 
Subject is permanently discontinued from further study drug administration.
	

NSAID = nonsteroidal anti-inflammatory drug.

Note: Appropriate resuscitation equipment should be available in the room and a physician readily available during the period of drug administration.

5.4.9. Criteria for Permanent Discontinuation of Study Drug

The occurrence of an unacceptable toxicity not caused by the underlying malignancy will be presumed to be related to study drug and will require that the study drug be permanently discontinued. Unacceptable toxicity is defined as follows:

- Grade 4 or life-threatening AEs (see [Table 4](#) and [Table 6](#)).
- \geq Grade 2 ocular irAE.
- Occurrence of an AE that is related to treatment with the study drug that, in the judgment of the investigator or the sponsor's medical monitor, compromises the subject's ability to continue study-specific procedures, or is considered to not be in the subject's best interest.
- An AE requiring more than 2 dose reductions of study drug, or more than 1 dose reduction of study drug if the starting dose is 0.03 mg/kg (see [Table 2](#)).
- Persistent AE requiring a delay of study drug beyond 4 weeks (28 days), unless the delay has been approved by the sponsor.

5.4.10. Treatment After Initial Evidence of Radiologic Disease Progression

Immunotherapeutic agents may produce antitumor effects by potentiating endogenous cancer-specific immune responses. The response patterns seen with such an approach may extend beyond the typical time course of responses seen with cytotoxic agents and may manifest as a clinical response after an initial increase in tumor burden or even the appearance of new lesions.

If radiologic imaging shows disease progression, then subjects have the option to continue treatment while awaiting radiographic confirmation of progression as outlined in [Section 7.7.1.1](#).

5.5. Withdrawal of Subjects From Study Drug

5.5.1. Withdrawal Criteria

A subject may choose to withdraw from the study at any time or be withdrawn from the study by the investigator or sponsor, if the subject is noncompliant with the study requirements. Subjects may also be withdrawn at the discretion of the FDA or health authorities. If a subject is withdrawn, then every reasonable effort should be made to determine the reason for withdrawal, and this information should be recorded in the electronic case report form (eCRF).

Subjects **must** be withdrawn from **study drug** for the following reasons:

- The subject becomes pregnant.
- Consent is withdrawn. Subjects may choose to withdraw from the study at any time without penalty of jeopardizing their health care or loss of benefits to which the subject is otherwise entitled.
- Further participation would be injurious to the subject's health or well-being, in the investigator's medical judgment.
- The subject is lost to follow-up.

- Unacceptable toxicity (see [Section 5.4](#)). Subjects with unacceptable toxicities must be withdrawn from study drug but will continue to be followed during the safety follow-up visits as specified in [Section 6.4](#).
- The study is terminated by the sponsor.
- The study is terminated by the local health authority, IRB, or IEC.

A subject **may** be discontinued from **study drug** as follows:

- Confirmed radiographic progression of disease per mRECIST v1.1. See [Section 7.7.1](#).

Note: For unconfirmed progression, see [Section 7.7.1](#).

Note: A subject may be granted an exception to continue on treatment with confirmed radiographic progression if clinically stable or clinically improved. See [Section 7.7.1](#).

- If, during the course of the study, a subject is found not to have met eligibility criteria (see [Section 3](#)), then the medical monitor, in collaboration with the investigator, will determine whether the subject should be withdrawn from the study.
- If a subject is noncompliant with study procedures or study drug administration in the investigator's opinion, then the sponsor should be consulted for instruction on handling the subject.

5.5.2. Withdrawal Procedures

In the event that the decision is made to permanently discontinue the study drug, the subject will be withdrawn from the study, and the end-of-treatment (EOT) visit should be conducted. Reasonable efforts should be made to have the subject return for follow-up visits. These visits are described in [Section 6](#). The last date of the last dose of study drug and the reason for subject withdrawal will be recorded in the eCRF.

If a subject is withdrawn from the study:

- The study monitor or sponsor must be notified.
- The reason(s) for withdrawal must be documented in the subject's medical record and in the eCRF.
- The EOT visit should be performed.
- The date of the EOT visit should be recorded in the IWRS.
- Subjects must be followed for safety until the time of the follow-up visit or until study drug–related toxicities resolve, return to baseline, or are deemed irreversible, whichever is longest.

If the subject discontinues study drug and actively withdraws consent for collection of follow-up data (safety follow-up or disease assessment), then no additional data collection should occur; however, subjects will have the option of withdrawing consent for study drug but continuing in the follow-up period of the study for safety/efficacy assessments.

5.6. Concomitant Medications

All concomitant medications and treatments must be recorded in the eCRF. Any prior medication received up to 28 days before the first dose of study drug and 60 days after the last dose of study drug will be recorded in the eCRF. Any addition, deletion, or change in the dose of these medications will also be recorded. Concomitant medications administered after 60 days after the last dose of study drug should be recorded for SAEs as defined in [Section 8](#).

Concomitant treatments/procedures that are required to manage a subject's medical condition during the study will also be recorded in the eCRF.

5.6.1. Permitted Medications

All treatments that the investigator considers necessary for a subject's welfare may be administered at the discretion of the investigator in keeping with the community standards of medical care. All concomitant medications will be recorded on the eCRF, including all prescription, over-the-counter, herbal supplements, and IV medications and fluids. If changes occur during the study period, documentation of drug regimen, frequency, route, and date may also be included on the eCRF. **Note:** The use of bisphosphonates and denosumab are permitted in this study.

5.6.2. Restricted Medications

Use of systemic glucocorticoids is restricted to prophylaxis for contrast allergies for radiographic procedures, or to modulate symptoms or treat an AE of suspected immunologic etiology. The use of physiologic corticosteroid replacement therapy may be approved after consultation with the sponsor.

Note: Inhaled and topical steroids are allowed. A short course of steroids (prednisone or equivalent) ≤ 10 mg/day may be permitted with sponsor approval.

- Acetaminophen and nonsteroidal anti-inflammatory agents (NSAIDs; eg, ibuprofen) may be used. Due to the risk of liver injury with the use of high doses of acetaminophen, subjects should be advised to stay within the recommended daily dose of acetaminophen.

5.6.3. Prohibited Medications

Medications or vaccinations specifically prohibited in the exclusion criteria (see [Section 3.2](#)) are not allowed during the ongoing study. If there is a clinical indication for one of these medications or vaccinations specifically prohibited during the study, discontinuation from study drug or vaccination may be required. The investigator should discuss any questions regarding this with the sponsor. The final decision on any supportive therapy or vaccination rests with the investigator and/or the subject's primary physician. However, the decision to continue the subject on study drug or vaccination schedule requires the mutual agreement of the investigator, the sponsor, and the subject.

Subjects are prohibited from receiving the following therapies during the screening and treatment periods of this study:

- Any anticancer medications, including chemotherapy or biologic therapy other than the study drug.
- Any immunological-based treatment for any reason from screening through follow-up visit.
Note: Completed adjuvant therapy (eg, vaccines) with medical monitor approval, inhaled or topical steroids, systemic steroids at doses ≤ 10 mg/day prednisone or equivalents, and immune suppressants are allowed for treatment of immune toxicities as described in [Section 5.4.7](#) and [Appendix B](#).
Note: Allergy shots may be permitted after consultation with the medical monitor.
- Investigational agents other than the study drug from screening through the follow-up visits.
- Concomitant radiation therapy.
Note: Radiation therapy to a symptomatic solitary lesion or to the brain may be considered on an exceptional case-by-case basis after consultation with the medical monitor. The subject must have clear measurable disease outside the radiated field. Administration of palliative radiation therapy will be considered clinical progression for the purposes of determining PFS.
- Live vaccines within 30 days before the first dose of study drug and while participating in the study. Examples of live vaccines include, but are not limited to, the following: measles, mumps, rubella, chicken pox, yellow fever, rabies, Bacillus Calmette–Guérin, and typhoid (oral) vaccine. Seasonal influenza vaccines for injection are generally killed virus vaccines and are allowed. However, intranasal influenza vaccines (eg, FluMist[®]) are live attenuated vaccines and are not allowed.

Subjects who, in the assessment by the investigator, require the use of any of the aforementioned treatments for clinical management should be removed from the study. Subjects may receive other medications that the investigator deems to be medically necessary. The exclusion criteria describe other medications that are prohibited in this study. There are no prohibited therapies during the post-treatment follow-up period.

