#### 8.1. General Considerations

Summary tables may be replaced with listings when appropriate. For instance, an AE frequency table may be replaced with a listing if it only contains a few unique PTs reported on relatively few subjects. Data from the Part 1 portion will be summarized separately where appropriate. Additional summaries for specific subgroups may be included on an ad hoc basis.

Unless otherwise stated, table summaries will be limited to AEs occurring within 60 days of the last administration of study drug.

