#### 8.2.4. Immune-Related Adverse Events

The number of subjects with irAEs and type of irAE will be listed by dose level and dose administration schedule for the Part 1 FAS population and by tumor type in the Part 1 Safety Expansion and Part 2 FAS population. Adverse event terms will be reviewed periodically without respect to treatment group by the medical monitor and clinical scientist to determine which AE terms correspond to irAEs. This periodic review may also occur after database lock. The medical monitor and clinical scientist will also review investigator reported AEs to determine if they qualify as irAEs. For example, a rash will be counted as an irAE even if the investigator did not report it as an irAE.

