| Subjects who had an irAE                    | xx (xx.x)      | xx (xx.x)      | xx (xx.x)     | xx (xx.x)     |
| Subjects who had a Grade 3 or higher irAE   | xx (xx.x)      | xx (xx.x)      | xx (xx.x)     | xx (xx.x)     |

FOLDER\PROGRAM\OUTPUT: XXXXXX\XXXXXX.SAS\XXXXXX.LST

Immune-Related Adverse Event: any AE consistent with an immune phenomenon associated with drug exposure after all other etiologies have been eliminated.

Treatment-Emergent Adverse Event: any AE either reported for the first time or worsening of a pre-existing event after first dose of study medication.

Treatment-Related Adverse Events: treatment-emergent adverse events judged as related by the investigator or with a missing causality.

DATABASE VERSION: XXXXX2016

DATE (TIME): MMDDYYYY (hh:mm)

PROTOCOL: INCAGN 1876-101

DRUG/INDICATION: INCAGN01876/Advanced or Metastatic Solid Tumors

TLF VERSION: Draft

Table 3.2.1.1

Overall Summary of Treatment-Emergent Adverse Events (Population: Part 1 FAS Population)

|   |               | Dose Lev      | el (mg/kg)    |                |       |
|---|---------------|---------------|---------------|----------------|-------|
|   | 1.0
(N=xx) | 3.0
(N=xx) | 5.0
(N=xx) | 10.0
(N=xx) | Total |
| Subjects who had a TEAE   | xx (xx.x)     | xx (xx.x)     | xx (xx.x)     | xx (xx.x)      |       |
| Subjects who had a treatment-related TEAE                             | xx (xx.x)     | xx (xx.x)     | xx (xx.x)     | xx (xx.x)      |       |
| Subjects who had a SAE  | xx (xx.x)     | xx (xx.x)     | xx (xx.x)     | xx (xx.x)      |       |
| Subjects who had an AE of grade 3 or higher                           | xx (xx.x)     | xx (xx.x)     | xx (xx.x)     | xx (xx.x)      |       |
| Subjects who had a fatal AE   | xx (xx.x)     | xx (xx.x)     | xx (xx.x)     | xx (xx.x)      |       |
| Subjects who had AE leading to
discontinuation of study medication | xx (xx.x)     | xx (xx.x)     | xx (xx.x)     | xx (xx.x)      |       |
| Subjects who had a DLT  | xx (xx.x)     | xx (xx.x)     | xx (xx.x)     | xx (xx.x)      |       |
| Subjects who had an irAE  | xx (xx.x)     | xx (xx.x)     | xx (xx.x)     | xx (xx.x)      |       |
| Subjects who had a Grade 3 or higher irAE                             | xx (xx.x)     | xx (xx.x)     | xx (xx.x)     | xx (xx.x)      |       |

FOLDER\PROGRAM\OUTPUT: XXXXXX\XXXXXX.SAS\XXXXXX.LST

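### Protocol 5.6.3 contradicts itself on therapies in follow-up, the SAP adverse event tables have no cut or flag at new anticancer therapy, and the sponsor's immune-related event list may change after database lock

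*Protocol*

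**What the plan says.** **Therapies in follow-up.** Protocol 5.6.3 opens its list with "Subjects are prohibited from receiving the following therapies during the screening and treatment periods of this study". Two bullets run longer than that: "Any immunological-based treatment for any reason from screening through follow-up visit" and "Investigational agents other than the study drug from screening through the follow-up visits". The section then closes with "There are no prohibited therapies during the post-treatment follow-up period".

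**Adverse event window.** SAP 8.1 states that, unless otherwise specified, "table summaries will be limited to AEs occurring within 60 days of the last administration of study drug". SAP 8.2.1 treats an adverse event as treatment-emergent (a TEAE) unless it is clear beyond doubt that it is not. It defines treatment-related events as a separate subset, set by the investigator's causality judgement, and counts a causality that stays missing as related.

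**Immune-related adverse events (irAEs).** Under SAP 8.2.4 the medical monitor and clinical scientist decide which event terms are irAEs and may count an event that the investigator did not. Of the term review it says "This periodic review may also occur after database lock". Its illustration is that "a rash will be counted as an irAE even if the investigator did not report it as an irAE". The footnote to shell Table 3.2.1.1 defines an irAE as "any AE consistent with an immune phenomenon associated with drug exposure after all other etiologies have been eliminated".

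**The concern.** The primary endpoint is the frequency, duration and severity of adverse events, so the safety tables are the main product of the study. Three features weaken how they can be read.

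- Sites cannot tell from 5.6.3 whether another immunotherapy or investigational drug is allowed once treatment has stopped. A subject who takes one may or may not have received a prohibited medication.
- If a subject starts a new drug inside the 60-day window, a later event is tabulated in the same way as one that occurred with INCAGN01876 as the only therapy, and nothing in the table shows the difference.
- The set of terms that the sponsor counts as irAEs need not be fixed when the data are locked. In an open-label study it can then be revised by people who have seen the results, with no record required.

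**Working it through.** No plan figure needs to be reproduced. The check sets the passages side by side, with one line of arithmetic on scale.

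**Step 1: can the statements in 5.6.3 be read together?**

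| Text in Protocol 5.6.3 | Period covered |
|---|---|
| Lead-in to the list | Screening and treatment only |
| Immunological treatment bullet | Through the follow-up visit |
| Investigational agents bullet | Through the follow-up visits |
| Closing sentence | Nothing barred in post-treatment follow-up |

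They would agree only if post-treatment follow-up began after the safety visits. Protocol Table 7 puts both safety follow-up visits under its Post-Treatment heading, and Protocol 4.4 has the subject enter follow-up as soon as treatment ends. So the two bullets conflict with both the lead-in and the closing sentence. SAP 5.3.4 names Section 5.6.3 as the basis for reviewing prohibited medications, so per protocol membership can depend on which sentence is applied.

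**Step 2: does anything remove or mark events after a new drug?**

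- Protocol 6.4.1 and 7.5 foresee new anticancer therapy before the 30-day or 60-day visit and move the visit ahead of it. Protocol 6.4.1 still requires event reporting to at least 60 days after the last dose, so collection does not stop when the visit is brought forward.
- SAP 8.1 and 8.2.1 contain no cut and no flag at new therapy. An event after the new drug still follows the first dose of INCAGN01876, so it meets the TEAE definition.
- The irAE tables in SAP Appendix A (3.2.18 to 3.2.21) are titled as treatment-emergent, not treatment-related. The investigator's causality judgement therefore does not filter them. The same holds for the Grade 3 or higher TEAE tables and the Kaplan-Meier analysis of time to first Grade 3 or higher TEAE.
- SAP Table 5 censors progression-free survival at new anticancer treatment. The start date is thus already needed for efficacy but is not used for safety.

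**Step 3: which outputs can a post-lock review change?**

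- The sponsor-identified tables (3.2.19.1 and 3.2.19.2) can change.
- So can Tables 3.2.20.1, 3.2.20.2 and 3.2.21.1, whose shells carry the sponsor-identified note. Table 3.2.21.2, the Part 2 counterpart of 3.2.21.1, carries no such note.
- The irAE rows of the overall summaries (3.2.1.1 and 3.2.1.2) and the Kaplan-Meier analysis of treatment-related Grade 3 or higher irAEs do not say whose classification applies.
- The investigator-identified tables (3.2.18.1 and 3.2.18.2) do not depend on the sponsor's review.

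**Step 4: scale.** Change in a cohort's rate per subject counted or not counted = 1/n.

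- Cohort stopped at Stage 1: 1/9 = 11.1 percentage points.
- Full cohort: 1/17 = 5.9 percentage points.
- All of Part 2 at its maximum: 1/68 = 1.5 percentage points.

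These use the planned evaluable numbers. SAP 5.3.3 pools eligible Part 1 subjects of the same tumor type, which would enlarge the denominators and shrink the steps.

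**The case against.** **Treatment-emergent is a timing label.** A reader might infer that the SAP charges every event to Day 60 to study drug. It does not. Relatedness is a separate, investigator-judged subset with its own tables, SAP 8.2.5 also plans counts of treatment-related irAEs, and only an unresolved missing causality defaults to related. This stands, and it confines the point to outputs not restricted by causality.

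**An irAE is a diagnosis of exclusion.** Reviewers who apply the footnote's definition would leave out an event explained by another drug, so it does not follow that such an event must be counted as an irAE. That is right. But SAP 8.2.4 begins from a review of terms and states no check for exposure to another drug.

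**The rash sentence is an illustration.** A reader might infer that every rash is counted as an irAE. The sentence only shows that the sponsor may count what the investigator did not, and Protocol Appendix B takes signs of dermatitis as immune-mediated unless another cause is found. The documents do not support the stronger reading.

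**Lock is not an unblinding point here.** In a single-drug, open-label study the reviewers already see the data, so a freeze removes only some of the scope for bias. The separate investigator-identified tables and listings also make a divergence visible. Both points have force. What remains is that a later change would leave no trace, and that several irAE outputs do not name their source.

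**The consequences are bounded.** All efficacy and safety analyses use the full analysis set (SAP 5.3.1), so the per protocol effect is small. SAP 3.3 calls all analyses exploratory. Escalation decisions rest on events through Day 28 (Protocol 5.4.2), although SAP 8.2.3 leaves room to consider later ones.

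**Conclusion.** The point holds in three limited parts.

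1. Protocol 5.6.3 contradicts itself on immunological treatment and investigational agents during follow-up. The passages must be reconciled; this review takes no view on which rule is right.
2. TEAE and treatment-emergent irAE tables can include events that began after another anticancer drug was started, and nothing marks them. Bringing the safety visit forward limits this only in part. The treatment-related tables are filtered by investigator judgement.
3. The sponsor's irAE classification may be changed after database lock without a required record.

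The total effect cannot be sized. It would need the share of subjects starting new therapy within 60 days and their irAE frequency on it. The documents give neither, so any overall percentage-point figure would be a product of two guesses. What can be said is the step per subject: 5.9 points in a full cohort and 11.1 in one stopped at Stage 1, assuming the planned evaluable numbers are the denominators. The Simon two-stage response rule is untouched.

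**What to change.** - **Protocol 5.6.3:** reconcile the lead-in, the two bullets and the closing sentence, and let SAP 5.3.4 follow the reconciled text.
- **SAP 8.1 and 8.2.1:** flag events with onset on or after the first new anticancer therapy. Take the start date from the data that SAP Table 5 already needs; Protocol 7.5 says that new therapy is reviewed but does not itself say that a date is recorded. Show irAE rates and Grade 3 or higher TEAE rates with and without the flagged events.
- **SAP 8.2.4:** freeze the sponsor's irAE term list before database lock and list any later change separately.
- **Table shells:** state under each irAE table whether the sponsor or investigator classification was used, and print the definition applied.

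The cost is a protocol wording change, some SAP text, one flag and one extra set of summaries. The irAE review must also finish before lock.
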